5.6. HEALTHY MOUTH vs DISEASE MOUTH CRITERIA

The differentiation between a healthy mouth and a diseased mouth will be made through a detailed observation and a clinical examination carried out by a dentist. This will be done in accordance with the guidelines of the World Health Organization (WHO; [https://www.who.int/publications/m/item/draft-global-oral-health-action-plan-\[2023-2030\]](https://www.who.int/publications/m/item/draft-global-oral-health-action-plan-[2023-2030])).

The signs that indicate a healthy mouth are:

- Firm, pink gums that do not bleed during brushing or flossing.
- Clean teeth without stains, without cavities or fractures.
- Absence of pain or dental sensitivity.
- No presence of bad breath or halitosis.
- No signs of inflammation or infection in the gums or around the teeth.

On the other hand, the signs that indicate a sick mouth are:

- Red, swollen or bleeding gums.
- Teeth with stains, cavities or fractures.
- Tooth pain or sensitivity, especially when biting or chewing food.
- Bad breath or chronic halitosis.
- Presence of abscesses or infections in the teeth or gums.

In the present study, based on these criteria, the dentist will make the diagnosis of "without oral cavity disease" or "with oral cavity disease" for each subject.

5.7. SUBJECT IDENTIFICATION

Patients will be identified with a sequential numerical identification code, which will be assigned to each patient according to the correlative order of inclusion when they give their informed consent. In the event that a patient is included in the study and is considered unfit to continue in the study or the patient withdraws their consent, the code assigned to that patient cannot be reused for the next consecutively assigned patient.

The promoter will only be able to identify the subjects by the code that has been assigned to them, their date of birth, sex and date of signing the informed consent. The principal investigator will keep a record, protected by password, with the names of the patients and the assigned identification code.

6. DEVELOPMENT OF THE TRIAL AND EVALUATION OF THE RESPONSE

6.1. ASSESSMENT OF EFFICACY

Not applicable.

6.2. SAFETY ASSESSMENT

Not applicable.

6.3. DEVELOPMENT OF THE TEST

Selection of patients and survey. Participants will attend the recruitment appointment after fasting for at least 8 hours. After verifying that they meet the inclusion and exclusion criteria and sign the informed consent, they will be given a survey that collects data on affiliation and lifestyle habits related to health and daily oral hygiene, including smoking and alcohol consumption; medical history that includes the medication taken, last visit to the dentist and risk factors and symptoms of oral disease, through questions that are easy to answer when self-identifying general symptoms compatible with gingivitis, periodontitis and dental caries (eg localized tooth sensitivity and in gums, bleeding gums, loose teeth, hypersensitivity in teeth to cold and/or heat, persistent bad breath, elongated teeth with receding and/or separated gums, modified bite, dry mouth, change of color in teeth, etc.).

Collection of salivary and blood samples. After completing the medical history, all patients will have their anthropometric data such as height, weight, waist circumference, hip circumference, systolic blood pressure, and diastolic blood pressure recorded. The research team dentist will perform a complete oral health diagnosis on the study subjects, using the World Health Organization (WHO) guidelines for diagnosing oral cavity disease ^{29,30}. Likewise, the oral health questionnaire will be passed. After the oral examination, **saliva** samples will be collected under resting conditions using the passive drooling method, in 15 mL tubes, every 1 min, for 5 min in the same tube. Together with the saliva samples, trained personnel will collect 9 ml of **blood samples**, under resting conditions, in EDTA tubes. The tubes will be centrifuged and the supernatant will be collected and stored at -80°C in the Biobank.

Analysis and detection of eCBs levels and profile of inflammatory biomarkers. In saliva and plasma, the analysis and detection of endocannabinoids and related lipids (2-arachidonoyl-glycerol [2-AG], N- arachidonoylethanolamine [AEA], N- palmitoylethanolamine [PEA], N- oleoylethanolamine [OEA], N- docosahexanoylethanolamine [DHEA], 2-linoleoylglycerol, [2-LG] and 2-oleoylglycerol [2-OG]). The analysis and detection of these factors will be carried out by HPLC chromatography. Inflammatory markers will also be quantified in saliva and plasma (interleukin [IL]-1 β , IL-6, IL-8, IL-10, IL-17, leptin, adiponectin, vascular endothelial growth factor [VEGF], Interferon [IFN]- γ and Tumor Necrosis Factor [TNF]- α), using Procarta multiplex assay (ThermoFisher Scientific) following the manufacturer's instructions. In addition, biochemical parameters such as blood glucose, insulin, HbA1c, triglycerides, total cholesterol, HDL cholesterol, LDL cholesterol will be analyzed in the hospital laboratory in the blood samples .

Analysis of oral bacteriological profiles. The bacteriological profiles in the saliva samples will be analyzed using massive sequencing techniques and amplification of the bacterial 16S rRNA amplicon of the following microbial strains: *Aggregatibacter actinomycetemcomitans*, *Porphyromonas gingivalis*, *Tannerella forsythia*, *Treponema denticola*, *Prevotella intermedia*, *Fusobacterium nucleatum*, *Parvimonas micra*, *Campylobacter rectus*, *Eikenella corrodens*, *Veillonella parvula* and *Actinomyces naeslundii* for periodontal diseases ; and *streptococci mutans* , *S. sanguis*, *S. mitior*, *S. salivarius* and *S. milleri* for tooth decay. In addition, saliva will be analyzed for sialometry (salivary flow), salivary viscosity, salivary pH and the impact profile on oral health (OHIP-14sp; WHO questionnaire).

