4. STUDY DESIGN

4.1. TYPE OF STUDY

Descriptive observational study.

A study with four groups is proposed: a group of obese diabetic subjects with a healthy mouth, a group of obese diabetic subjects with a diseased mouth, a group of obese pre-diabetic subjects with a healthy mouth, and a group of obese pre-diabetic subjects with sick mouth. All patients will be recruited on a voluntary and unpaid basis. After a meeting with each participant, where a detailed explanation about the study will be given, written informed consent will be obtained, as well as the necessary information to complete the medical evaluation questionnaire, which will allow determining their state of health and the criteria of inclusion and exclusion. Once the patient's eligibility is confirmed, they will be scheduled to fast for a saliva and blood extraction and an oral health questionnaire and/or an oral clinical examination.

The samples of the patients included in the study will be processed and frozen at -80°C until their subsequent analysis following standardized protocols. The samples will be stored in the biobank of the Hospital Regional de Málaga-IBIMA, which is part of the biobank of the public health system of Andalucía (BSSPA).

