5.2. SAMPLE SIZE

Based on previous publications that have reported the levels of endocannabinoids in saliva (20), at least 12 subjects are needed to detect as significant differences of 0.5pmol/ml of AEA and 25pmol/ml of 2-AG, which are the differences found between healthy people and obese people. It is intended to recruit 15 people with obesity, prediabetes and a healthy mouth, 15 people with obesity, prediabetes and a diseased mouth, 15 people with obesity, diabetes and a healthy mouth, and 15 people with obesity, diabetes and diseased mouth. To differentiate a healthy mouth from a diseased mouth, a complete oral evaluation will be carried out on all participants, which includes a review of the mucous membranes, an evaluation of the bacterial plaque and the presence of dental caries, and an evaluation of the health of the teeth, gums, including the depth of probing and the presence of gingival bleeding (see point 5.6).

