5.4. EXCLUSION CRITERIA

- Pregnant women
- Diagnosis of some type of neoplasia or treatment with radiotherapy and/or chemotherapy in the last year.
- Ongoing inflammatory diseases (Crohn's disease, ulcerative colitis, arthritis, etc.) and/or anti-inflammatory treatments
- Presence of systemic diseases of vital organs
- Participants in treatment with drugs that could alter salivary flow
- Smokers.
- Participants who have not followed the specifications prior to sampling
- Participants who did not sign the informed consent

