5.5. ELIMINATION CRITERIA

- Inadequate amount of saliva to perform the tests

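### Saliva is taken after an examination that probes the gums, so salivary outcomes may differ by oral disease status partly because of the sampling order

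*Protocol*

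**What the plan says.** - **Order.** Section 6.3 describes the dentist's complete oral diagnosis, then the questionnaire ("Likewise, the oral health questionnaire will be passed"), then the saliva sample: "After the oral examination, saliva samples will be collected under resting conditions using the passive drooling method". It reads as a single appointment.
- **Content of the examination.** Section 5.2 says all participants have a complete oral evaluation, "including the depth of probing and the presence of gingival bleeding (see point 5.6").
- **Group definition.** Section 5.6 lists "Red, swollen or bleeding gums" among the signs of a diseased mouth. Gums that do not bleed on brushing or flossing are a sign of a healthy one.
- **Sampling safeguards.** Section 5.4 excludes "Participants who have not followed the specifications prior to sampling", but the protocol does not list those specifications. The only elimination criterion in section 5.5 is "Inadequate amount of saliva to perform the tests".
- **Visit structure.** Section 4.1 says of eligible patients that "they will be scheduled to fast for a saliva and blood extraction and an oral health questionnaire and/or an oral clinical examination". This list fixes neither the order nor whether examination and sampling share a visit.
- **Planned difference.** Section 5.2 states that "at least 12 subjects are needed to detect as significant differences of 0.5pmol/ml of AEA and 25pmol/ml of 2-AG". The plan is for four groups of 15 (sections 1.10 and 5.2), compared by ANOVA with post-tests at the 5% level (section 7.2).

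**The concern.** Probing can release blood, crevicular fluid and dislodged plaque into the mouth shortly before the saliva is collected. Everyone has the same examination, but the response to it is unlikely to be the same in both arms of the comparison, because bleeding gums help to define the diseased mouth. The procedure that classifies the participant may then also change the specimen on which the classes are compared.

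The main objective (section 1.6) is the difference by presence or absence of OCD. Endocannabinoids and cytokines are measured in both saliva and plasma, so blood in the saliva is a plausible carrier of the same analytes. The bacterial profile could be altered by released plaque, and salivary flow, which section 7.1 wants unstimulated, by the handling of the mouth. This cannot be left to the analysis: once the samples are frozen, their order cannot be changed.

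**Working it through.** **1. Does anything else in the protocol neutralise the order?**

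| Possible safeguard | Where | Does it settle the matter? |
|---|---|---|
| Collection at rest | 6.3 | No. It concerns stimulation, not material already released, and no interval is given. |
| Questionnaire mentioned between examination and saliva | 6.3 | No. It may create a pause, but no duration or order is fixed. |
| Centrifugation of the tubes | 6.3 | Unclear whether saliva tubes are covered. It would remove cells and debris, not soluble blood components. |
| Pre-sampling specifications | 5.4 | Not listed. |
| Elimination rule | 5.5 | Saliva amount only; visible blood is not mentioned. |
| Recorded bleeding; salivary protein | 5.2; 7.1 | Bleeding status allows a sensitivity analysis and protein is at most a crude marker. Neither cleanly separates procedure from disease. |

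**2. Can the planned difference be put on a standard scale?** The stated 12 cannot be reproduced, because section 5.2 gives no standard deviation (SD), power or sidedness, and does not say whether 12 is per group or in total. I solved backwards for the standardised difference d from the two-sided 5% t-test (noncentral t, 2n − 2 df, noncentrality d·√(n/2)):

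- 12 per group, 80% power: d = 1.197
- 12 per group, 90% power: d = 1.385
- 12 in total (6 per group), 80% power: d = 1.796

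**3. What would an artefact do if there were no true difference?** Let the artefact be a fraction x of the planned difference, that is, a shift of x·d SD in the OCD groups.

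- *One 15 v 15 comparison*, uncorrected t-test, 28 df: noncentrality x·d·√(15/2). For x = 0.25 and d = 1.197 this is 0.299 × 2.739 = 0.82, which gives a rejection rate of 12.4%.
- *Four-group ANOVA*, 15 per group, both OCD groups shifted: noncentral F on 3 and 56 df, noncentrality 60·(x·d/2)². For x = 0.25 this is 60 × 0.1496² = 1.34, which gives 13.4%.

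| Assumption | x = 0.10: t / ANOVA | x = 0.25: t / ANOVA | x giving 10%: t / ANOVA |
|---|---|---|---|
| d = 1.197 | 6.2% / 6.2% | 12.4% / 13.4% | 0.206 / 0.197 |
| d = 1.385 | 6.6% / 6.6% | 15.0% / 16.7% | 0.178 / 0.170 |
| d = 1.796 | 7.6% / 7.8% | 22.1% / 26.0% | 0.137 / 0.131 |

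A simulation of the ANOVA at d = 1.197 (40,000 runs) gave 6.1% and 13.4% for x = 0.10 and 0.25.

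**4. Back to units, at d = 1.197.** 0.206 × 0.5 = 0.103 pmol/ml AEA and 0.206 × 25 = 5.15 pmol/ml 2-AG (t-test). With 0.197 the figures are 0.099 and 4.93 (ANOVA).

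A pooled comparison of 30 with OCD against 30 without would be more sensitive: the fraction that doubles the error rate falls to 0.143 at d = 1.197.

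**The case against.** The strongest reply is that the decisive step is not in the protocol. It says that probing is done and that bleeding gums are a sign of disease. It does not say that probing changes salivary endocannabinoids, cytokines or flow, by how much, or in which direction. Every participant has the same examination, so the mechanical stimulation is not differential by design. OCD can also be diagnosed from cavities, fractures, stains, pain or halitosis without bleeding. Bleeding that is already present belongs to the disease; only the extra release caused by probing is artefact. All of this stands, and it is why the point is a likely difference on average, of unknown size.

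The scale calculation has limits too. The 0.5 and 25 pmol/ml are differences between healthy and obese people, not between people with and without OCD. Using one d for both analytes assumes equal standardised differences. The figures do not carry over directly if data are logged or tested non-parametrically, as section 7.2 allows. They show how large an artefact would have to be, not that one of that size exists.

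Intervals or rinses may exist in local procedures, since section 4.1 refers to standardised protocols for processing and analysis, but the protocol shows none. A stated interval, a recorded blood check or a separate visit would also help. None of these objections reverses the order that section 6.3 fixes or makes it preferable to sampling first.

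**Conclusion.** The concern holds. As written, the plan takes the saliva after a procedure that is likely to disturb it more in the groups with OCD, and nothing in the protocol prevents or measures this cleanly. The size and direction of the effect are unknown: the protocol gives no analyte levels and no amount of blood released.

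For scale only, an artefact of about one fifth of the planned difference would double the 5% false-positive rate. This assumes 12 per group, 80% power, a two-sided test and no true difference. The fraction falls to about 0.13 if the 12 is a total. An artefact of opposite sign could instead hide a true difference. Plasma results are not affected by this route.

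This should be fixed. The main reason is that the remedy is cheap and the harm cannot be undone after sampling; the illustrative error rates are secondary. Confidence is medium because the size is unknown.

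**What to change.** In section 6.3, change the saliva sentence so that collection takes place before the oral examination instead of after it. State the same order in section 4.1, and say there whether examination and sampling take place at the same visit. This removes the contribution of the examination. It does not remove spontaneous gum bleeding, which is part of the disease.

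If both are done at the one appointment that section 6.3 describes, only the order changes, with no extra visit, staff or procedure for the participant. The cost is that OCD status is known only after sampling, so some saliva samples, and the 9 ml of blood taken with them, may go unused once a group of 15 is full. That number cannot be estimated, because the protocol gives no OCD prevalence for its source population.

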7. STATISTIC ANALYSIS

7.1. COLLECTED VARIABLES

The following groups of variables are included in this essay:

- Anthropometric data: weight, height, body mass index, waist circumference, hip circumference, blood pressure.
- Clinical data: Previous or ongoing illnesses, current medication.
- Blood test data: Standard biochemistry (plasma glucose, insulin, plasma HbA1c, lipid profile, renal function, liver function, lymphocytes, hs-CRP, etc.), inflammatory markers (panel of inflammatory cytokines, including IL-6 , IL-1beta, and TNF-alpha), endocannabinoids (2-AG, AEA, PEA, OEA, DHEA, 2-LG, 2-OG).
- Saliva data: Salivary flow (to calculate unstimulated oral saliva flow), salivary viscosity, salivary pH, salivary protein concentration. Inflammatory markers (panel of inflammatory cytokines , including IL-6, IL-1beta and TNF-alpha), endocannabinoids (2-AG, AEA, PEA, OEA, DHEA, 2-LG, 2-OG), Bacteriological profiles. In addition, the oral health impact profile (OHIP-14sp) will be evaluated, both through the dental examination and through questions.

7.2. STATISTICAL ANALYSIS

For the statistical study, the statistical software package SPSS 25.0 will be used. A database equivalent to the data collection notebook will be created with all the variables. First, the sample will be studied (descriptive statistics) using absolute and relative frequencies and then inferential statistics will be performed. The parametricity of the variables will be studied using a normality test. The parametric analysis will be carried out using ANOVA, followed by the corresponding post-test analysis. If the distribution of the variable is not normal, it will be converted to log or a non-parametric test will be used to contrast the differences. All hypothesis contrasts will be made with a significance level of 5%.

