1.6. MAIN OBJECTIVE OF THE TRIAL

Investigate the possible differences in endocannabinoid levels and their correlation with inflammatory cytokines and microbial load in the oral cavity depending on the presence or absence of oral cavity disease in people with obesity and prediabetes or diabetes.

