1.10. STUDY POPULATION AND TOTAL NUMBER OF PATIENTS

A total of 60 adult patients are expected to be included: 15 diagnosed with obesity and prediabetes with OCD, 15 diagnosed with obesity and prediabetes without OCD, 15 diagnosed with obesity and diabetes with OCD, and 15 diagnosed with obesity and diabetes without OCD.

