3.4. AIMS

Based on this hypothesis, we propose the following main objective: **to study the possible differences in the levels of cannabinoids (2-AG, AEA, PEA, OEA, DHEA, 2-LG, 2-OG; pmol/ml), both in saliva and plasma, in a sample of patients with/without oral cavity disease, and with obesity and prediabetes, or with obesity and T2D.**

As secondary objectives will be studied:

- The bacteriological profile of the oral cavity (increase in the bacterial 16S rRNA amplicon, compared to the reference genes, for the following bacterial strains: *Aggregatibacter actinomycetemcomitans*, *Porphyromonas gingivalis*, *Tannerella forsythia*, *Treponema denticola*, *Prevotella intermedia*, *Fusobacterium nucleatum*, *Parvimonas micra*, *Campylobacter rectus*, *Eikenella corrodens*, *Veillonella kindergarten* and *Actinomyces naeslundii* for periodontal disease; and *streptococci mutans*, *S. sanguis*, *S. mitior*, *S. salivarius* and *S. milleri* for dental caries).

- Inflammatory cytokines in saliva and plasma (interleukin [IL]-1 β , IL-6, IL-8, IL-10, IL-17, leptin, adiponectin, vascular endothelial growth factor [VEGF], Interferon [IFN]- γ and Tumor Necrosis Factor [TNF]- α).

- Glucose management through fasting blood glucose levels (mg/dL), insulin (mUI/mL), HbA1c (%), HOMA-IR, HOMA2-IR, QUICKY, HOMA2%S, HOMA2%B.

- Adiposity and atherogenic profile, through BMI (kg/m²), waist circumference (cm), waist/hip ratio, waist/height ratio, blood pressure (mmHg), triglycerides (mg/dL), total cholesterol (mg/dL), HDL cholesterol (mg/dL), LDL cholesterol (mg/dL), total cholesterol/HDL, LDL/HDL, and Triglycerides/HDL ratios.

- Salivary parameters (sialometry (salivary flow), salivary viscosity, salivary pH and the impact profile on oral health (OHIP-14sp; WHO questionnaire)).

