5. SUBJECT SELECTION

5.1. STUDY POPULATION

A population of patients of both sexes aged 40-65 years, with obesity and diagnosed with pre-diabetes, and with obesity and diabetes, and who meet the rest of the inclusion criteria, as well as who do not present any of the criteria, will be studied. of exclusion, and who agree to participate voluntarily in the study. For this, three studies led by our unit will be based on: The Pizarra study, an epidemiological study of the UGC of Endocrinología y Nutrición del Hospital Regional de Málaga that has provided detailed information on anthropometric, biochemical, eating habits and style parameters. of life in a cohort of about 1,700 subjects, the [contact] study, a national epidemiological study carried out on a sample of more than 5,000 people, coordinated by this Unit, and the April study, a nutritional intervention study on people with obesity and prediabetes. In addition, the databases of the obesity consultations of the UGC of Endocrinología y Nutrición del Hospital Regional de Málaga will be available. Based on these databases, we will proceed to contact the people who could meet the inclusion criteria, in order to arrange a recruitment visit for the study, following the guidelines of the Declaration of Helsinki (Fortaleza 2013) and the Standards of Good Clinical Practices. Personal data will be processed in accordance with REGULATION (EU) 2016/679 OF THE EUROPEAN PARLIAMENT AND OF THE COUNCIL of April 27, 2016 on the protection of natural persons with regard to the processing of personal data and the free movement of these dates; and Organic Law 3/2018, of December 5, Protection of Personal Data and guarantee of digital rights

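### Section 7.2 names neither its ANOVA model nor any adjustment, though the main question is OCD present v absent; an adjusted two-way model would answer it with all 60 participants

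*Protocol*

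**What the plan says.** **Design.** Protocol section 4.1 states: "A study with four groups is proposed". Section 1.10 gives the sizes: "15 diagnosed with obesity and prediabetes with OCD, 15 diagnosed with obesity and prediabetes without OCD", and the same two groups of 15 for diabetes. The groups are therefore a 2x2 of OCD by glycaemic status, with 30 people on each side of the OCD question.

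**Question.** The main objective in section 1.6 concerns differences "depending on the presence or absence of oral cavity disease in people with obesity and prediabetes or diabetes". Section 3.4 words it as differences in endocannabinoid levels "in a sample of patients with/without oral cavity disease, and with obesity and prediabetes, or with obesity and T2D". That also puts OCD first, but it can be read as a comparison of four groups.

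**Analysis.** Section 7.2 says: "The parametric analysis will be carried out using ANOVA, followed by the corresponding post-test analysis". For a variable that is not normally distributed, "it will be converted to log or a non-parametric test will be used to contrast the differences". On the error rate, "All hypothesis contrasts will be made with a significance level of 5" per cent. It names no factor, interaction, covariate, primary contrast or particular post-test.

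**How the groups arise.** Section 5.1 recruits from existing databases: "we will proceed to contact the people who could meet the inclusion criteria". Section 5.6 has a dentist classify each person as with or without OCD. No randomisation or matching is described. Age is restricted to 40-65 and BMI to 30-40, and smokers are excluded (sections 5.3 and 5.4).

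**The concern.** An analysis should deliver the comparison that the objective asks for. With four groups followed by post-tests, the natural software route is a one-way ANOVA and up to six pairwise comparisons. Only two of the six compare OCD with no OCD inside the same glycaemic stratum, and each uses half the participants. No test then uses all 60 people for OCD.

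Two things are at stake. First, precision and interpretation: two separate half-size tests of one common effect will often disagree, and the disagreement invites the claim that OCD matters only in prediabetes or only in diabetes. Second, bias: OCD status is observed, so people with and without it may differ in age or sex even within the eligibility limits. Any such difference passes into an unadjusted comparison. The log or non-parametric fallback in 7.2 settles neither point.

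**Working it through.** **Inputs.** From the protocol: 4 cells of 15 and a 5% level (taken as two-sided). Error degrees of freedom are 60 - 4 = 56. The protocol gives no SD, power or post-test, so effects are in SD units (d), and unadjusted and Tukey post-tests are both shown. All figures are for one endocannabinoid in one fluid.

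**The protocol's own figure.** Section 5.2 states that at least 12 subjects are needed to detect 0.5 pmol/ml of AEA and 25 pmol/ml of 2-AG. This cannot be reproduced without an SD and a power, but it can be solved backwards. If 12 is per group, with two-sided 5% and 80% power, d = (1.96 + 0.84) x sqrt(2/12) = 1.14. The implied SDs are 0.5/1.144 = 0.44 and 25/1.144 = 21.9 pmol/ml.

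**Standard errors, in SD units.**
- OCD effect averaged over strata (30 v 30): sqrt(1/15) = 0.258.
- One OCD pair (15 v 15): sqrt(2/15) = 0.365.
- Ratio: sqrt(2) = 1.41, whatever the value of d.

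**95% CI half-widths.** The critical t on 56 df is 2.003; for Tukey with four groups it is 2.648.
- Averaged contrast: 2.003 x 0.258 = 0.52 SD.
- Unadjusted pair: 2.003 x 0.365 = 0.73 SD.
- Tukey pair: 2.648 x 0.365 = 0.97 SD.

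**Power.** Noncentral t, with noncentrality d x sqrt(15) for the averaged contrast and d x sqrt(7.5) for a pair. The either-pair and exactly-one figures come from 400,000 simulated trials with the same OCD effect in both strata.

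| | d = 0.8 (assumed) | d = 1.14 (12 per group) |
|---|---|---|
| Averaged OCD contrast | 86% | 99% |
| One pair, unadjusted | 58% | 87% |
| One pair, Tukey | 33% | 69% |
| At least one pair, unadjusted | 81% | 98% |
| At least one pair, Tukey | 55% | 89% |
| Exactly one pair, unadjusted | 48% | 23% |
| Exactly one pair, Tukey | 43% | 42% |

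A hand check of the exactly-one row at d = 0.8, treating the pairs as independent: 2 x 0.577 x 0.423 = 0.49 and 2 x 0.333 x 0.667 = 0.44. These are close to the simulated values; the pairs share one error variance.

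Counting either unadjusted pair as success has a price. With no OCD effect, at least one pair is significant in 9.7% of trials if no overall F test is required first.

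**Lack of adjustment.** The bias from an age imbalance, in SD units of the outcome, is the age gap (in SD) times the age-outcome correlation. The protocol gives neither, so the following is illustration only. Gaps of 0.5 to 1.0 SD with correlations of 0.2 to 0.4 give shifts from 0.5 x 0.2 = 0.10 to 1.0 x 0.4 = 0.40 SD. With no true OCD effect, an unadjusted 30 v 30 contrast would then be significant in 7% to 33% of trials instead of 5%. Pooling the strata does not cure this; adjustment does.

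**The case against.** **The model may be set in a SAP that is not shown.** Factors and covariates often are. This stands in part: 7.2 neither states a one-way model nor excludes a two-way one or adjustment. A reader might infer that the protocol commits to one-way ANOVA. It does not. Four groups describes the cells of a 2x2 just as well, and cell comparisons are also run after two-way models. But 7.2 is not silent. It states a method, and a likely way of carrying it out misses the OCD contrast.

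**Four-group comparison may be the intended question.** Section 3.4 permits this, recruitment is set by cell, and the study is called descriptive. If OCD acts in one stratum only (0.8 SD), the averaged contrast has 33% power, against 57% for the overall F test and 60% for either unadjusted pair. This stands, and is why within-stratum estimates must be kept.

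**The effect of 0.8 SD is not the protocol's.** True. At 1.14 SD little power is lost if either pair counts. If the 12 subjects are a total (6 per group, d about 1.62), either-pair power exceeds 99% and the pairs disagree in only 2% to 8% of trials. A reader might infer that the study is underpowered for OCD. The documents do not show that.

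**The confounding sizes are invented.** They are assumptions, and 33% is the extreme corner. Eligibility limits and equal cell sizes remove some imbalance, including imbalance in glycaemic status. A reader might infer that the OCD comparison will be confounded. The protocol shows only that nothing in the stated analysis protects against it.

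**Conclusion.** The point holds as a weakness of specification that should be corrected before analysis; it is not an arithmetic error. What rests on the protocol alone is this: the objective concerns OCD, the design is a 2x2, the OCD groups are neither assigned nor matched, and 7.2 names no model, OCD contrast or adjustment.

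The loss of precision is conditional on a one-way analysis with pairwise post-tests. On that condition the 1.41-fold standard error is exact for full cells of 15, before any post-test correction. The consequence depends on an effect size that the protocol does not fix: substantial at 0.8 SD, small in power terms at 1.14 SD if either pair counts. Disagreement between the pairs is the more persistent problem under Tukey, at about 42% even at 1.14 SD. The size of any bias from age or sex imbalance cannot be known from the protocol. Confidence is medium, because the one-way reading is inferred.

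**What to change.** In section 7.2, state that each endocannabinoid is analysed by a two-way linear model with OCD, glycaemic status and their interaction, adjusted for age and sex, on the log scale where the section's own rule calls for it. Name the OCD effect averaged over the two glycaemic strata as the main contrast. Report the interaction and the two within-stratum OCD estimates alongside, all with confidence intervals. Keep any non-parametric test as a sensitivity check.

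This is a change of wording. Date of birth and sex are already recorded (section 5.7), and the model runs in the planned software. The two covariates cost 2 degrees of freedom. At d = 0.8, power goes from 86% to 85% if they explain nothing, and rises to 88% or 91% if they explain 10% or 20% of the variance (assumed). Under the strongest age imbalance illustrated above, adjusted power is 82%. The remaining cost is the lower power of an averaged contrast when OCD acts in one stratum only, which the within-stratum estimates are there to reveal.
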